5.7.2.3. Change of Hemoglobin Level and Transfusion Burden

The mean change in hemoglobin level from baseline over 8- or 12-week period in NTD patients and the mean % change from baseline in transfusion burden over an 8- or 12-week period in TD patients will be summarized. In addition, the mean change in pre-transfusion hemoglobin levels in TD patients (including analysis of patient subset with $< 20\%$ change in transfusion burden) will also be analyzed. Summary statistics will be presented for these parameters.

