10.2.3. RBC Transfusions

Concurrent treatment for anemia with blood transfusions is allowed, at the discretion of the investigator, for low hemoglobin levels, symptoms associated with anemia (e.g., hemodynamic or pulmonary compromise requiring treatment) or comorbidity.

For any RBC transfusions (NTD or TD patients) received during the study, collect hemoglobin values just prior to transfusion.

Each TD patient will have a defined “pre-transfusion hemoglobin threshold” which will be calculated based on transfusion history and will be used for determining when to transfuse during the study. The baseline pre-transfusion hemoglobin threshold will be the mean of all documented pre-transfusion hemoglobin values during the 12 weeks prior to C1D1 of base study A536-04 (for patients without treatment interruption) or study A536-06 (for patients with treatment interruption). During treatment, if the pre-transfusion hemoglobin level is increased by ≥ 1 g/dL compared to the baseline pre-transfusion hemoglobin threshold for that patient, transfusion should be delayed by a minimum of 7 days and/or the number of units transfused should be reduced by 1 or more RBC units. Patients may be transfused at the investigator’s discretion for symptoms related to anemia or other requirements (e.g., infection). Patients may be transfused on the same day as ACE-536 is administered except on C1D1 for patients with treatment interruptions.

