10.4. Randomization

This study does not require randomization and is open-label.

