15.2.3. Secondary Analysis

All efficacy analyses will be performed for the EE and mITT populations.

Efficacy will be evaluated by determining the proportion of β -thalassemia patients who have an erythroid response, defined as 1) a mean hemoglobin increase ≥ 1.0 g/dL or ≥ 1.5 g/dL over an 8-week or 12-week period as compared to baseline, not influenced by RBC transfusion in NTD patients or 2) $\geq 20\%$ or $\geq 50\%$ reduction in RBC transfusion burden over an 8-week or 12-week period as compared to the 8-week or 12-week period pretreatment in TD patients.

Baseline hemoglobin for NTD patients will be the average of two or more measurements performed during the screening period for base study A536-04 (for patients without treatment

interruption) or study A536-06 (for patients with treatment interruption). Hemoglobin measurements within 2 weeks following RBC transfusion will be excluded.

Transfusion burden for TD patients will be defined as the ratio of RBC transfusion units (or mLs) transfused during an interval divided by the duration of that interval, where the interval may be during the pretreatment period or the treatment plus follow-up period. The interval during the pretreatment period will be defined as the 8 or 12 weeks prior to Cycle 1 Day 1 of base study A536-04 (will also be analyzed using pretreatment period of study A536-06 for patients with treatment interruption). An interval during the treatment plus follow-up period will be defined as an 8-week or 12-week interval after Cycle 1 Day 1 of study A536-06.

The erythroid response, as defined above, will also be evaluated using other pre-treatment and on-treatment intervals and other % reductions in RBC units transfused, including 100% (transfusion-free).

The erythroid response will be summarized using both a point estimate and its exact 95% CI based on binomial distribution.

No direct comparison testing with concurrent or historical controls will be performed.

Analysis of other secondary efficacy/PD endpoints will include:

- Time to erythroid response and duration of erythroid response
- Change/percent change from pretreatment in mean transfusion burden in TD patients
- Change in mean hemoglobin level in NTD patients
- Change in pre-transfusion hemoglobin levels in TD patients (including analysis of patient subset with < 20% change in transfusion burden)
- Change from baseline in erythropoiesis parameters, including EPO, reticulocytes, nucleated RBCs, and soluble transferrin receptor

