3.3. Sample Size

There is no formal sample size calculation for the study although up to 64 patients may participate from the A536-04 study.

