5.2. General Considerations

Unless otherwise noted, continuous data will be summarized with the following descriptive statistics: number of observations (n), mean, standard deviation (STD), minimum, median, and maximum. Categorical data will be summarized with frequencies (n) and percentages (%). In cases where missing data cause percentages not to sum to 100, a missing data row will be provided. Percentages will use column totals as the denominator unless otherwise indicated. For time to event variables, the Kaplan-Meier curves will be presented if the number of patients is more than 5.

All study data will be included in study data listings. Missing data will generally be treated as missing, not imputed, unless otherwise stated.

Data summaries may also be presented for TD and NTD patients separately as specified. All summaries will be descriptive. No formal hypothesis testing is planned.

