- The proportion of patients who have $\geq 33\%$ reduction in RBC transfusion burden compared to pretreatment using rolling 24-week intervals
- The proportion of patients who have $\geq 50\%$ reduction in RBC transfusion burden compared to pretreatment using rolling 24-week intervals
- The proportion of patients who have $\geq 33\%$ reduction in RBC transfusion burden compared to pretreatment during weeks 37-48
- The proportion of patients who have $\geq 50\%$ reduction in RBC transfusion burden compared to pretreatment during weeks 37-48
- The proportion of patients who have no RBC transfusions ≥ 8 weeks

For each of the above defined erythroid response rates, a point estimate will be presented along with the exact 95% confidence interval based on binomial distribution.

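### TD response is scored on RBC units alone, and no planned summary shows whether the responders were transfused at a lower hemoglobin than before treatment

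*SAP*

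**What the plan says.** **Design.** Protocol 10.4: "This study does not require randomization and is open-label". Protocol 15.2.3: "No direct comparison testing with concurrent or historical controls will be performed". SAP 5.2: "All summaries will be descriptive. No formal hypothesis testing is planned".

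**Response.** SAP 5.7.2.1 defines TD response as a reduction of at least 20%, 33% or 50% in RBC burden against pretreatment, over rolling 8-, 12- or 24-week intervals or in fixed weeks 13–24 and 37–48. It also has a transfusion-free item, "The proportion of patients who have no RBC transfusions" for at least 8 weeks. Protocol 15.2.3 defines burden as units (or mL) per interval. No definition contains a hemoglobin condition.

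**When to transfuse.** Under protocol 10.2.3 each TD patient has a pre-transfusion hemoglobin threshold, the mean of the documented values over the 12 weeks before C1D1, which "will be used for determining when to transfuse during the study". The one explicit action tied to it is to delay or reduce transfusion when hemoglobin is at least 1 g/dL above it. No tolerance below it is stated. The same section opens: "Concurrent treatment for anemia with blood transfusions is allowed, at the discretion of the investigator, for low hemoglobin levels".

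**What is analysed.** SAP 5.7.2.3: "In addition, the mean change in pre-transfusion hemoglobin levels in TD patients (including analysis of patient subset with" less than 20% change in transfusion burden). SAP 5.6.2 lists pre-transfusion values by patient. SAP 5.7 drops hemoglobin values within 14 days after a transfusion from efficacy derivations unless specified otherwise.

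**The concern.** A before-and-after count of RBC units measures drug effect only if patients are transfused at a comparable hemoglobin in both periods. If an unblinded investigator lets hemoglobin run lower before transfusing, units fall and the SAP records a response.

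The check that would reveal this is pre-transfusion hemoglobin in the patients counted as responders. The only subset the SAP names is patients whose burden hardly changed. That subset can show benefit in non-reducers, but it says nothing about whether the responders' reductions came at maintained hemoglobin. The summary over all TD patients includes responders, but a rise in non-reducers could offset a fall in responders. At stake is how the TD response rates, a secondary objective, can be read.

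**Working it through.** The plan has no figure to reproduce: SAP 3.3 states "There is no formal sample size calculation for the study although up to 64 patients may participate from the A536-04 study". What follows is an illustration of sensitivity.

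**Inputs from the documents.** The TD minimum is 4 units per 8 weeks (SAP 5.1). Its programming form, 11 units in 26 weeks, is 11/26 × 12 = 5.1 per 12 weeks. Response cut-offs are 20%, 33% and 50%.

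**Step 1: units that must be saved.**

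| Pretreatment units | ≥20% | ≥33% | ≥50% |
|---|---|---|---|
| 4 per 8 weeks | 1 (25%) | 2 (50%) | 2 (50%) |
| 6 per 12 weeks | 2 (33%) | 2 (33%) | 3 (50%) |
| 10 per 12 weeks | 2 (20%) | 4 (40%) | 5 (50%) |

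**Step 2: a trigger model with no drug effect.** Assumptions, none in the documents: 2 units per transfusion raise hemoglobin by 2 g/dL; pretreatment trigger H = 9.5 g/dL; exponential decline toward a plateau P of 4 to 6 g/dL; perfectly regular transfusions. Let T be the pretreatment spacing, d the drop in trigger, and u the days from the last pretreatment transfusion to Day 1, uniform on 0 to T. With L = ln[(H+2−P)/(H−P)]:

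- new spacing T′ = T × ln[(H−d+2−P)/(H−d−P)] / L
- one-off delay D = T × ln[(H−P)/(H−d−P)] / L
- on-study transfusions fall on day T−u+D and every T′ days after
- steady-state reduction = 1 − T/T′: 15.7% (P=4) to 23.1% (P=6) for d=1.0; 23.5% to 34.8% for d=1.5

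**Step 3: first 12 weeks (84 days).**

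- *4 units per 8 weeks (T=28, so 6 units before), d=1.0.* P=4: L=0.3102, D=18.12, T′=33.20. Transfusions fall at 46.1−u, 79.3−u and 112.5−u; the third is always after day 84, so 6→4 (33%) in 100% of timings. P=6: D=20.84, T′=36.41. The second, at 85.26−u, is inside unless u<1.26, so 6→4 in 26.74/28 = 96%.
- *Same patient, d=1.5.* P=4: the second transfusion, at 93.35−u, is outside when u<9.35, so 6→2 (67%) in 9.35/28 = 33%. P=6: at 105.61−u, outside when u<21.61, so 77%.
- *6 units per 8 weeks (T=18.67), d=1.0.* 84/18.67 = 4.5, so the pretreatment count is 10 when u<9.33 and 8 otherwise. From 10, three transfusions remain: 10→6 (40%), in half of timings. From 8, the result is 6 or 8, at most a 25% reduction.

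**Step 4: 8-week and rolling intervals.** At the TD minimum with d=1.0, the second transfusion falls after day 56 when u<23.3 (P=4, 83% of timings) or always (P=6), giving 4→2. For rolling 12 weeks, three gaps of 33.2 days span 99.6 days, so some 84-day interval holds only two transfusions (4 units against 6). This rolling result is sharp because 3 × 28 is exactly 84; irregular spacing alone could also produce it.

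**Step 5: fixed weeks 13–24, d=1.5, reduction of at least 50%.**

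- T=28, P=4: T′=36.60, and 2 × 36.60 = 73.2 < 84, so at least two transfusions always fall inside: 0%.
- T=28, P=6: T′=42.94, and 2 × 42.94 = 85.88, so only one falls inside in 1.88/28 = 7%.
- T=18.67, P=4: T′=24.40, and 3 × 24.40 = 73.2 < 84, so at least 6 units against 8 or 10: 0%.
- T=18.67, P=6: T′=28.63, and three gaps again span 85.88 days, so 1.88/18.67 = 10%.

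The range is 0–10%. This covers only the 50% cut-off. At 33% with d=1.0 and T=28, 6→4 in weeks 13–24 needs u<10.9 at P=4 (39% of timings), or u between 1.26 and 26.49 at P=6 (90%).

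**Step 6: a cruder cross-check.** Take one-off savings only, with an assumed rise of 0.6–1.2 g/dL per unit. Saving 1 unit needs a drop of 0.6–1.2 g/dL, 2 units 1.2–2.4, 3 units 1.8–3.6 and 5 units 3.0–6.0. A 50% reduction over 12 weeks therefore needs 1.8–3.6 g/dL from 6 units or 3.0–6.0 from 10. This ignores the continuing saving in Step 2, but agrees that 50% over 12 weeks is harder to reach than 20% over 8 weeks.

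**The case against.** The strongest reply is that transfusion is not left uncontrolled. The protocol says the threshold governs when to transfuse, so a sustained lower trigger would depart from it. The discretion attached to symptoms or infection permits extra transfusions, which work against response. Pre-transfusion change is summarised for all TD patients, and values and response derivations are listed by patient. With at most 64 patients, a reader could check responders by hand. Safety is the primary objective and everything is descriptive.

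Much of this stands. A reader might infer that the trigger is uncontrolled, or that pre-transfusion hemoglobin is never checked; the threshold, the overall summary and the listings contradict both. The documents also give no evidence that triggers fell, or that opposite changes cancel in the overall mean.

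What remains is narrower. The threshold is an instruction for conduct whose explicit action runs upward only, and the SAP plans no analysis of adherence to it among responders. A listing permits inspection after the fact; it is not a prespecified summary. SAP 5.7.2.7 already splits LIC change by TD responder status, so the same split here is no departure from the plan's own practice.

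**Conclusion.** The point holds as a gap in the analysis, not as evidence of bias. Response from transfusing at a lower hemoglobin would count as erythroid response, and no planned summary or sensitivity analysis separates the two in responders.

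The size depends on the endpoint and on assumptions outside the documents. The ≥20% 8-week and ≥33% rolling 12-week definitions are most exposed, chiefly near the TD minimum. At 4 units per 8 weeks, a 1.0 g/dL lower trigger gives 6→4 in 96–100% of timings. At 6 units per 8 weeks, 10→6 occurs in about half. A 1.5 g/dL drop at the TD minimum gives 6→2 in 33–77%. A reduction of at least 50% in weeks 13–24 is little affected (0–10%). It would be wrong to infer that every response rate is equally open to doubt, or that a 1 g/dL shift readily yields a 50% response over 12 weeks: in this model it does so in at most about 4% of timings at the TD minimum (1.26/28).

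**What to change.** Change the analysis only; no transfusion or dosing rule is touched.

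- **SAP 5.7.2.3.** By TD responder status, summarise pre-transfusion hemoglobin in the qualifying interval minus the patient's 12-week baseline threshold. Do this for the ≥20% 8-week definition and for ≥33% and ≥50% over 12 and 24 weeks. Exempt these values from the 14-day exclusion in SAP 5.7, which would otherwise drop them in patients transfused every 14 days or less.
- **SAP 5.7.2.1.** Add a sensitivity response rate with exact 95% CI that does not count an interval whose mean pre-transfusion hemoglobin is 1 g/dL or more below the baseline threshold. This mirrors the margin the protocol uses above it.
- **Transfusion-free intervals.** Report scheduled-visit hemoglobin separately, noting that it is not the same quantity as a pre-transfusion value.
- **No documented baseline value.** Report these patients as not assessable, because the baseline rests on documented history.

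On-study pre-transfusion values are already collected (protocol 10.2.3). The cost is SAP wording, one table and a sensitivity rate that may be lower than the headline rate. If triggers held, the table strengthens the reported response.

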5.7.2.4. Iron-Related Parameter Analysis

Selected iron metabolism parameters will be taken at Day 1 of Cycles 1, 5, 9, 13, 17, 21, Day 1 of every 4 subsequent cycles until cycle 85, EOT, and EOS visits. Descriptive statistics of actual

values, absolute and percentage change from baseline values at each post-baseline time point will be presented. A shift table will be produced for ferritin from baseline to post-baseline.

Plots of iron parameters (serum iron, TIBC, transferrin, calculated transferrin saturation, ferritin, NTBI) for both mean observed values and mean absolute change from baseline over time will be presented.

5.7.2.5. Erythropoiesis Parameters

Erythropoiesis parameters include serum EPO levels, reticulocytes, nucleated RBCs, soluble transferrin receptor, hemoglobin electrophoresis, and folate.

EPO will be taken at Day 1 of Cycle 1, Days 1 and 8 of Cycles 5, 9, 13, 17, Day 1 of every 4 subsequent cycles until cycle 85, EOT, and EOS. Reticulocytes and nucleated RBCs will be taken at Screening, Days 1 and 8 of Cycles 1, 3, 5, 7, 9, 11, 13, 15, 17, Day 1 of Cycles, 2, 4, 8, 10, 12, 14, 16 and Cycles 18 to 87, EOT and EOS visits. Soluble transferrin receptor will be taken at Day 1 of Cycles 1, 5, 9, 13, 17, Day 1 of every 4 subsequent cycles until Cycle 85, EOT, and EOS. Hemoglobin electrophoresis will be taken at Day 1 of Cycles 1, 5, 13, 21, 29, 37, 45, 53, 61, 69, 77, EOT, and EOS. Serum folate will be taken at screening for patients with treatment interruption to confirm eligibility, and required at Day 1 of Cycles 1, 5, 13, 21, 29, 37, 45, 53, 61, 69, 77, and EOT.

Descriptive statistics of observed values, absolute and percentage change from baseline values at each post-baseline visit will be presented for all patients. Plots of erythropoiesis parameters for mean observed values, mean change, and mean percentage change from baseline over time will be presented.

5.7.2.7. Liver Iron Content (LIC)

MRI for liver iron content (LIC) will be performed. Descriptive statistics of actual values, absolute and percentage change from baseline at post-baseline visits will be presented. The summary will be done by NTD/TD, baseline LIC ≥ 3 and < 3 mg/g dw subgroups and baseline iron chelation therapy (ICT) use (yes vs. no) respectively.

LIC responses will be defined as LIC reduction ≥ 1 mg/g dw at post-baseline visits compared with baseline. LIC response rates along with the exact 95% confidence interval will be estimated for NTD and TD patients respectively, as well as by baseline LIC ($<$ or ≥ 3 mg/g dw) and baseline ICT use (yes vs. no). As an exploratory analysis, LIC change from baseline will be summarized by TD responders and non-responders, where TD responder is defined as 33% reduction in rolling 24 week and 50% reduction in rolling 12 weeks, respectively.

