10.2.2. Other Treatments for β -Thalassemia

If treatment with hydroxyurea is required during the ACE-536 treatment period, the patient should be discontinued from treatment with study drug and complete the EOT visit and enter the follow-up period. Iron chelation therapy is allowed if initiated at least 56 days prior to C1D1. If iron chelation therapy is required during study treatment, patient should follow standard of care for management of iron chelation therapy.

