- Change from baseline in hemolysis parameters, including total/indirect bilirubin, and LDH
- Change from baseline in iron overload and iron metabolism parameters, including serum iron, total iron binding capacity (TIBC), transferrin, calculated transferrin saturation, soluble transferrin receptor, ferritin, non-transferrin bound iron (NTBI), hepcidin, iron chelation therapy use and LIC by MRI

The exploratory endpoints will include evaluation of biomarkers related to the TGF- β superfamily, quality of life, change in EMH mass size, change in spleen size, change in BMD, change in leg ulcer size, and change in the 6MWT distance in NTD patients.

All binary endpoints will be summarized using both a point estimate and its exact confidence interval based on the binomial distribution. The time-to-event type secondary endpoints will be

analyzed using Kaplan-Meier method to estimate the survival curve and median time to event and 95% CI.

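### The SAP accounts for iron chelation only at baseline for liver iron and not at all for ferritin, and it drops the protocol's chelation-use endpoint

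*SAP*

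**What the plan says.** **LIC.** SAP 5.7.2.7 states: "The summary will be done by NTD/TD, baseline LIC ≥ 3 and < 3 mg/g dw subgroups", and adds "baseline iron chelation therapy (ICT) use (yes vs. no) respectively". It then states: "LIC responses will be defined as LIC reduction ≥ 1 mg/g dw at post-baseline visits compared with baseline". Response rates with exact 95% intervals are given for NTD and TD patients, by baseline LIC and by baseline chelation use. The definition sets no condition on chelation received between baseline and the scan. As an exploratory analysis, "LIC change from baseline will be summarized by TD responders and non-responders".

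**Ferritin.** SAP 5.7.2.4 plans summaries by visit and plots, and states: "A shift table will be produced for ferritin from baseline to post-baseline". Chelation is not mentioned.

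**Chelation on study.** Protocol 10.2.2 states: "Iron chelation therapy is allowed if initiated at least 56 days prior to C1D1". It continues: "If iron chelation therapy is required during study treatment, patient should follow standard of care for management of iron chelation therapy". Protocol 10.1 caps dosing at 87 cycles or 1,825 days, whichever comes first.

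**Chelation as an endpoint.** The iron-overload item in Protocol 15.2.3, which covers change from baseline, ends with "hepcidin, iron chelation therapy use and LIC by MRI". The SAP has no matching analysis. Its table of changes (5.12.6) has two entries: the baseline hemoglobin definition, and the removal of the efficacy evaluable population with the renaming of mITT.

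**The concern.** Change in iron overload is a secondary objective, and the study has one arm. A reader will look to the stratum with no baseline chelation for a LIC effect of the drug free of chelators. As defined, that stratum can contain patients who were chelated for years before the scan that made them responders.

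The reverse case matters too. Protocol 7.1 presents less transfusion and less chelation as the hoped-for benefit. A patient whose chelator is cut back because fewer transfusions are needed may show no LIC fall and count as a LIC non-response, and no table would show the reduction in chelation. The exploratory comparison of TD responders with non-responders has the same weakness, because chelation may be adjusted as transfusion load changes.

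**Working it through.** The plan states no sample size, power or expected rate for LIC or ferritin, so there is no figure to reproduce. The check compares the texts; the arithmetic in step 4 is only an illustration.

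**1. Time in which chelation can change.** 1,825 / 365 = 5.0 years, and 60 months / 12 = 5 years. Cycle 87 Day 1 falls on day 1 + 86 × 21 = 1,807, which agrees with the schedule. LIC scans after C1D1 are planned at C9, C17, C25, C33, C41, C49, C57, C65, C73 and C81 (10 visits) plus EOT. For patients who roll over without interruption, SAP 5.1 takes the A536-04 baseline, so the base-study treatment period is added to the window.

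**2. The rules applied to three patients.**
- No chelator at baseline, starts one in year 2, LIC then falls by 1 mg/g dw or more: counted as a response in the no-chelation stratum.
- Chelated at baseline, dose raised, LIC falls by the same amount: counted as a response in the chelated stratum.
- Chelated at baseline, chelator reduced or stopped, LIC unchanged: counted as a non-response in the chelated stratum.

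In the no-chelation stratum the first change can only be a start. In the chelated stratum, and in the overall NTD and TD rates, changes in both directions can occur.

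**3. Where chelation appears in the SAP.** It is a baseline characteristic (5.4), a baseline split for LIC (5.7.2.7) and a prior-therapy subgroup for erythroid response (5.7.4). Chelators taken on study appear only in the general medication summary and listing (5.6.1), which is not linked to LIC or ferritin. No section tabulates change in chelation use.

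**4. Illustration with assumed inputs, none from the documents.** Let p be the LIC response rate with no chelation change, f the share of patients who start or intensify chelation, and r the share of those who reach the threshold because of it.

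Observed rate = p + (1 − p) × f × r

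| p | f | r | Observed | Shift (points) |
|---|---|---|---|---|
| 0% | 10% | 50% | 5.0% | +5.0 |
| 0% | 30% | 80% | 24.0% | +24.0 |
| 20% | 10% | 50% | 20% + 0.8 × 5% = 24.0% | +4.0 |
| 20% | 30% | 80% | 20% + 0.8 × 24% = 39.2% | +19.2 |

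For the opposite direction, let g be the share who reduce or stop and s the share of would-be responders among them who lose the response. Observed rate = p × (1 − g × s). With p = 20% and the same ranges for g and s, this gives 20% × 0.95 = 19.0% and 20% × 0.76 = 15.2%, shifts of −1.0 and −4.8 points.

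The exact interval does not cover this bias. With N = 64, the ceiling on enrolment, 13/64 has a 95% interval of 11.3% to 32.2% and 25/64 one of 27.1% to 52.1%. Both intervals describe sampling error only.

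**The case against.** **The analysis is descriptive.** The primary objective is safety and no hypothesis is tested. LIC observed under standard-of-care chelation is a legitimate summary. This stands: error rates are not affected and the planned rates should stay. It does not remove the problem of interpretation, because rates with exact intervals are reported by chelation stratum.

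**Chelators are already listed.** SAP 5.6.1 summarises and lists all medications, so a reader could match listings by hand. That is true, but no planned table makes the link.

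**Doses should be stable.** Protocol 10.2 speaks of stable doses for chronic conditions. Section 10.2.2 is the rule specific to chelation, and it defers to standard of care once chelation is required. Separately, 10.2.2 states its 56-day entry condition for all patients, whereas exclusion criterion 7 applies one only to patients with treatment interruption. These passages must be reconciled.

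**The endpoint was optional, or the omission minor.** The synopsis list of efficacy assessments says only that such parameters may be included, and SAP 5.12.6 covers only major changes. But the analysis list in Protocol 15.2.3 is not permissive, and Protocol 15.5 requires departures from the protocol's analyses to be indicated in the SAP.

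**Splitting by later chelation adds bias.** Chelation after baseline may itself respond to treatment, and patients who start a chelator are probably those whose iron is rising. This stands. It is why such a display belongs beside the planned rates and should not replace them.

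**Conclusion.** The point holds as an inexpensive improvement to the SAP. Three things follow from the texts without assumptions:
- LIC analyses account for chelation only through baseline use, and ferritin analyses not at all.
- The response definition would count a chelator-driven fall.
- A secondary endpoint listed in the protocol has no analysis and no recorded reason for its removal.

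Three stronger readings are tempting and are not supported:
- A reader might infer that the LIC response rate is inflated by a known amount. The documents give no rate of chelation change, the ranges above rest on invented inputs, and changes can act in both directions, so size and net direction are unknown.
- A reader might infer that baseline chelation is the only split for liver iron and ferritin. LIC is also split by NTD/TD and baseline LIC, with TD response as an exploratory split. Ferritin has no chelation split of any kind.
- A reader might infer that the planned rates should be replaced by rates restricted to periods before a chelator start or increase. That would select on events after baseline. It would also be one-sided, because values after a reduction or stop would remain.

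**What to change.** 1. **Restore the endpoint.** Add to the SAP the number and percentage of patients with chelation started or stopped during the study, for TD and NTD separately. Add dose increased or reduced only if the eCRF records chelator dose; the eCRF is not among the documents.
2. **Add displays beside the planned ones.** Keep the LIC response rates of 5.7.2.7 unchanged. Next to them show LIC change, LIC response and ferritin by on-study chelation status. Count changes from the same baseline as the LIC value (SAP 5.1), and apply the date-imputation rules in SAP 5.12.4.
3. **Add one sensitivity analysis.** Use only LIC and ferritin values from before any chelation change, in either direction. Label it descriptive because it conditions on an event after baseline.
4. **Record the change** in SAP 5.12.6.

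**Cost.** SAP text, one derived status variable and extra tables, with no new visits. Started and stopped can be derived from the medication dates that SAP 5.6.1 already uses. Some cells will be small: LIC MRI is optional and done at selected sites, and at most 64 patients are expected under the SAP.
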